**Table 3: Intrasubject Dose De-escalation by Assigned Daily Dose**

Assigned Daily Dose	420 mg (3 x 140 mg)	560 mg (4 x 140 mg)	840 mg (6 x 140 mg)
Dose De-escalation Level 1	280 mg (2 x 140 mg)	420 mg (3 x 140 mg)	700 mg (5 x 140 mg)
Dose De-escalation Level 2	140 mg (1 x 140 mg)	280 mg (2 x 140 mg)	560 mg (4 x 140 mg)

If complete resolution or improvement of the toxicity to Grade 1 or to baseline values is achieved within 28 days, the investigator may elect to have the subject restart treatment with study drug. If the toxicity takes more than 28 days to resolve, then discussion with the medical monitor is required prior to the subject restarting treatment with study drug. Upon restarting treatment with study drug, the investigator may elect to reduce the subject's dose of study drug by 1 dose level, or by 2 dose levels if previously dose reduced, if the toxicity is considered likely related to study drug and likely to recur at the subject's current daily dose. Otherwise, study drug should be restarted at their current daily dose.

### 6.5.2 Dose Modification for Hepatic Impaired Subjects

Ibrutinib is metabolized in the liver. For subjects who develop mild liver impairment while on study (Child-Pugh class A), the recommended dose reduction for ibrutinib is to a level of 280 mg daily (two capsules). For subjects who develop moderate liver impairment while on study (Child-Pugh class B), the recommended dose reduction is to a level of 140 mg daily (one capsule). Subjects who develop severe hepatic impairment (Child-Pugh class C) must hold study drug until resolved to moderate impairment (Child-Pugh class B) or better. Monitor subjects for signs of toxicity and follow dose modification guidance as needed (Refer to [Appendix 6](#)).

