#### **2.4.5 PCYC-1111-CA Stage 1 Summary**

As of 31 December 2013, a total of 69 subjects were enrolled in Stage 1: 13 subjects in Cohort 1, 18 subjects in Cohort 2, 18 subjects in Cohort 3 and 20 subjects in Cohort 4.

The observed safety profile across the four tested cohorts in this ongoing study did not indicate clinically meaningful differences and the overall obtained safety profile with ibrutinib alone or in combination is consistent with the reported treatment-emergent AEs detailed in the current version of the IB for PCI-32765.

Efficacy data collection is ongoing with 19 subjects still on treatment and 4 subjects treated for more than 6 cycles. The Simon 2-stage enrollment expansion criteria were met for Cohort 4 with 4 confirmed minimal responses (MR) and 9 subjects remaining on treatment.

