### *Laboratory*

17. Absolute neutrophil count (ANC) < 750 cells/ $\mu\text{L}$  ( $0.75 \times 10^9/\text{L}$ ) independent of growth factor support.
18. Platelet count < 50,000 cells/ $\mu\text{L}$  ( $50 \times 10^9/\text{L}$ ) independent of transfusion support.
19. Serum aspartate transaminase (AST) or alanine transaminase (ALT)  $\geq 3.0$  x upper limit of normal (ULN).
20. Total bilirubin > 2.5 x ULN, unless due to Gilbert's syndrome.
21. Creatinine > 2.5 mg/dL.

*Concurrent Conditions*

23. Major surgery within 2 weeks of the first dose of study drug.
24. Concomitant therapy with denosumab (bisphosphonate is allowed).
26. Currently active, clinically significant cardiovascular disease such as uncontrolled or symptomatic arrhythmias, congestive heart failure, or myocardial infarction within 6 months of screening, any Class 3 or 4 cardiac disease as defined by the New York Heart Association Functional Classification, or evidence of QT prolongation (QTc > 470 msec).
27. Unable to swallow capsules or disease significantly affecting gastrointestinal function, such as malabsorption syndrome, resection of the stomach or small bowel, or complete bowel obstruction.
28. History of prior malignancy, with the exception of the following:
  - a. Malignancy treated with curative intent and with no known active disease present for more than 3 years prior to screening and felt to be at low risk for recurrence by treating physician;
  - b. Adequately treated non-melanoma skin cancer or lentigo maligna without current evidence of disease; or
  - c. Adequately treated breast or cervical carcinoma in situ without current evidence of disease.
29. Peripheral neuropathy Grade  $\geq 2$  on clinical examination within 14 days prior to enrollment.
30. Uncontrolled diabetes mellitus.
31. Currently active systemic fungal, bacterial, viral, or other infection not controlled (defined as exhibiting ongoing signs/symptoms related to the infection and without improvement, despite appropriate antibiotics or other treatment).
32. Use of antibiotics for treatment of infection within 7 days prior to first dose of study drug.
33. Known history of infection with human immunodeficiency virus (HIV) or history of active infection with hepatitis C virus (HCV) or hepatitis B virus (HBV) or any uncontrolled active systemic infection.
34. History of stroke or intracranial hemorrhage within 6 months prior to the first dose of study drug.

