39. Requires anticoagulation with warfarin or a vitamin K antagonist (eg, phenprocoumon).
40. Requires treatment with strong CYP3A4/5 inhibitors (see [Appendix 2](#)).

*Ethical/Other*

35. Subject is pregnant or breastfeeding.
36. Will not agree to use highly effective contraception (eg, condoms, implants, injectables, combined oral contraceptives, some intrauterine devices [IUDs], sexual abstinence, or sterilized partner) during the study and for 30 days after the last dose of study drug. (Note: applies to women of childbearing potential or men with female partners of childbearing potential only.)
37. Any other life-threatening illness, medical condition or organ system dysfunction that, in the investigator's opinion, could compromise the subject's safety, or put the study outcomes at undue risk.
38. Any medical or psychiatric condition that, in opinion of investigator, could interfere with the subject's ability to give informed consent, compliance, or treatment.

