**6.3 Dosage and Administration****6.3.1 PCI-32765**

PCI-32765 140-mg capsules are intended to be administered orally once daily with 8 ounces (approximately 240 mL) of water (avoid grapefruit or Seville orange juice due to CYP450 3A4/5 inhibition). The capsules should be swallowed intact and subjects should not attempt to open

capsules or dissolve them in water. Subjects should refrain from taking the study drug on the morning of study visits designated for PK sampling until seen at the site (see [Section 7.1.2](#)). One cycle of treatment is once-daily administration of PCI-32765 for 28 days.

Dosages are as follows:

Cohort	PCI-32765 (mg/day)	Dexamethasone
1	420 (3 capsules)	Upon PD, 40 mg once weekly is allowed
2	560 (4 capsules)	40 mg once weekly
3	840 (6 capsules)	Upon PD, 40 mg once weekly is allowed
4	840 (6 capsules)	40 mg once weekly

Subjects will continue on study drug until PD, withdrawal of consent, or until discontinuation of study drug due to an AE. Subjects may continue study drug as long as the subject is deriving clinical benefit (SD or better) and the subject is not experiencing any unacceptable toxicity.

PCI-32765 capsules should be taken at approximately the same time each day. If a dose is missed, it can be taken as soon as possible on the same day with a return to the normal schedule the following day. The missed dose will not be made up and must be returned to the site at the next scheduled visit.

A subject diary will be used to aid with study drug administration compliance.

Only enough PCI-32765 capsules to supply subject until the next study visit should be dispensed with the exception of Cycle 1 where enough PCI-32765 capsules for the entire cycle can be dispensed. Unused PCI-32765 capsules dispensed during previous visits must be returned and drug accountability records ([Section 10.8](#)) updated according to the schedule in [Appendix 4](#).

Returned capsules must not be re-dispensed to the same subject or to another subject.

Investigators are prohibited from supplying PCI-32765 capsules to any subject not properly enrolled in this study or to any physician or scientist except those designated as subinvestigators on Form FDA 1572. The investigator must ensure that subjects receive PCI-32765 capsules only from personnel who fully understand the procedures for administering the study drug.

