#### **6.3.3.2 Concurrent Dosing of PCI-32765/Dexamethasone Combination (Cohorts 2 and 4)**

PCI-32765 will be administered orally once daily at dosages of 560 mg (Cohort 2) and 840 mg (Cohort 4). Dexamethasone 40 mg will be administered orally once weekly, starting Day 4 of Cycle 1. The rationale for this timing is to 1) prevent toxicity from dexamethasone confounding safety and tolerability as might occur if administered concurrently on Day 1, and 2) to allow intra-subject assessment of impact of dexamethasone on PCI-32765 PK.

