#### **6.3.3.3 Concurrent Dosing of PCI-32765/Dexamethasone Combination (Cohort 4 expansion)**

PCI-32765 will be administered orally once daily at a dose of 840 mg (6 x 140 mg capsules). Dexamethasone 40 mg will be administered orally once weekly, starting Day 8 of Cycle 1, following completion of the 7 hour postdose PK sample collection.

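### Section 5.2 sets no Child-Pugh limit and no starting dose covers pre-existing hepatic impairment, so a class B subject entering the Cohort 4 expansion could start at 840 mg, six times the 140 mg recommended for class B on study

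*Protocol*

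**What the plan says.** **On treatment.** Protocol Section 6.5.2 gives a hepatic dose rule for impairment that subjects develop after entry: class A goes to 280 mg, class C is held until it improves to class B or better, and for class B "For subjects who develop moderate liver impairment while on study (Child-Pugh class B), the recommended dose reduction is to a level of 140 mg" daily.

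**Starting dose.** Section 6.3.1 assigns 420, 560, 840 and 840 mg to Cohorts 1 to 4, with no hepatic qualification. Section 6.3.3.2 repeats this for the combination cohorts ("PCI-32765 will be administered orally once daily at dosages of 560 mg (Cohort 2) and 840 mg (Cohort 4"), and Section 6.3.3.3 does so for the Cohort 4 expansion ("PCI-32765 will be administered orally once daily at a dose of 840 mg (6 x 140 mg capsules").

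**Entry.** The laboratory exclusions in Section 5.2 remove AST or ALT at or above 3 times ULN (exclusion 19) and bilirubin above a limit (exclusion 20: "Total bilirubin > 2.5 x ULN, unless due to" Gilbert's syndrome). Exclusion 33 covers viral hepatitis. Exclusion 37 is general: it covers any "medical condition or organ system dysfunction that" the investigator believes could compromise safety. Inclusion 4 requires ECOG 0 or 1. No entry criterion mentions albumin, INR, ascites, encephalopathy or Child-Pugh class. Appendix 6 tabulates the score but attaches no entry rule to it.

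**Exposure.** Section 2.4.4 reports single-dose AUC increases of 2.7-, 8.2- and 9.8-fold in classes A, B and C.

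**The concern.** The protocol treats class B impairment as serious enough to cut the dose to one capsule when it appears during treatment. The same impairment present on Day 1 has no stated limit and no stated dose. Whether the subject is excluded or starts at the full cohort dose depends on how each investigator reads exclusion 37, so sites can differ.

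The protocol handles another cause of raised exposure at both ends. A need for strong CYP3A inhibitors is excluded at entry (exclusion 40), and Section 6.8.1.1 gives dose rules on treatment. Hepatic impairment has an explicit rule at one end only.

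What is at stake is patient safety. The operating characteristics of the Simon designs are not in question.

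**Working it through.** **1. The plan's own doses.** Capsules are 140 mg (Section 6.2). The cohort doses reproduce: 3 × 140 = 420, 4 × 140 = 560, 6 × 140 = 840 mg. The class B dose in Section 6.5.2 is one capsule, 140 mg.

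**2. Ratio of starting dose to the class B dose.**
- Cohort 1: 420/140 = 3
- Cohort 2: 560/140 = 4
- Cohorts 3 and 4: 840/140 = 6

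**3. Can a class B subject meet the numeric criteria?** Appendix 6 defines class B as 7-9 points. The order below is bilirubin + albumin + INR + ascites + encephalopathy, with no ascites and no encephalopathy.
- Normal bilirubin, albumin 2.8-3.5 g/dL, INR 1.71-2.30: 1 + 2 + 2 + 1 + 1 = 7. No assumption about ULN is needed.
- Bilirubin 2.0-2.5 mg/dL, normal albumin, INR 1.71-2.30: 2 + 1 + 2 + 1 + 1 = 7. This does not depend on albumin, which myeloma itself may lower.
- Bilirubin 2.0-2.5 mg/dL, albumin 2.8-3.5 g/dL, normal INR: 2 + 2 + 1 + 1 + 1 = 7.

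The documents give no bilirubin ULN, so the second and third routes need an assumption. Exclusion 20 allows up to 2.5 × ULN. A value of 2.0 mg/dL is eligible if ULN is at least 2.0/2.5 = 0.8 mg/dL, and the whole 2.0-2.5 range if ULN is at least 2.5/2.5 = 1.0 mg/dL.

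Exclusion 39 ("Requires anticoagulation with warfarin or a vitamin K antagonist") removes warfarin as the explanation for a raised INR in an enrolled subject.

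**4. Do later safeguards bring the dose to 140 mg?** The holds in Section 6.5.1 respond to toxicity, so they act after exposure. The lowest step in Table 3, divided by 140 mg, is:
- assigned 420 mg: 140/140 = 1 (reaches the class B dose)
- assigned 560 mg: 280/140 = 2
- assigned 840 mg: 560/140 = 4

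**5. How many subjects could still enter?** Section 2.4.5 reports that "The Simon 2-stage enrollment expansion criteria were met for Cohort 4" and says this of no other cohort. Twenty subjects had been enrolled in Cohort 4 by 31 December 2013, and its maximum is 43 (Table 1), so at most 43 − 20 = 23 more could follow.

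**The case against.** Much of the opposing case stands.

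- **Exclusion 37 already covers this.** Investigators have the 8.2-fold figure, the Child-Pugh table and the screening results, and most would probably not enrol a patient with evident class B disease. Exclusions 19, 20 and 33 and the ECOG limit narrow the group further. This makes such an entry unlikely, but it does not fix a class or a dose.
- **Section 6.5.2 could be applied by analogy.** A sensible investigator might do so. Its wording is limited to impairment that develops on study, and the cohort dosing sections make no exception.
- **Later safeguards exist.** Table 3 does reach 140 mg for an assigned 420 mg. A fourth occurrence leads to discontinuation (Table 2), and Section 6.6 requires withdrawal when the investigator judges it best for the subject. All of these follow exposure.
- **Enrolment may be over.** The count of 23 is dated. A cohort may close early at 8 responders (Section 8.5.2). The SAP rests on Amendment 5 of August 2015, and its version 4.0 of June 2016 describes the final analyses. The documents do not say that enrolment has closed, but the number an entry criterion could still protect may be zero.
- **The fix keeps some judgement.** Deciding whether liver disease is suspected, or whether low albumin is hepatic, remains with the investigator. The gain is a fixed class limit and a fixed action.

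A reader might infer that sites had no guidance at all. The documents do not support that: Section 6.8 refers to the Investigator's Brochure for complete precautions, and the Brochure is not available here.

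**Conclusion.** The gap is real and its practical size is minor. As written, the protocol lets a subject with pre-existing class B impairment meet every numeric entry criterion and start at the cohort dose. For the Cohort 4 expansion that is 6 times the dose recommended when class B arises on study. The ratios of 3 and 4 belong to Cohorts 1 and 2, which are not reported to have met their expansion criteria. The first scoring route rests on no assumption; the other two need a bilirubin ULN of about 1.0 mg/dL or more. The number affected is unknown and probably small, between none and 23 further entrants counted from 31 December 2013.

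Three stronger readings are tempting but unsupported.
- That class B subjects were enrolled or harmed: the documents contain no baseline Child-Pugh data.
- That 840 mg in class B equals 8.2 × 840 = 6,888 mg with normal liver function: the 8.2-fold figure is from single doses, and Section 2.4.4 reports proportionality only for 420 to 840 mg.
- That Section 2.4.4 shows more severe adverse reactions in class B: that sentence concerns mild impairment by NCI-ODWG criteria.

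**What to change.** Make two text changes.

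1. Add an exclusion to Section 5.2: *Pre-existing moderate or severe hepatic impairment (Child-Pugh class B or C, Appendix 6), scored at screening in subjects with known or suspected liver disease.* The bilirubin, albumin, PT/INR and physical examination that it needs are already part of screening (Sections 7.1.1 and 7.1.2).
2. In Section 6.5.2, for classes B and C, change *develop* to *had at baseline or develop*, so that class B goes to 140 mg and class C is held. This also covers subjects already on treatment, whether or not enrolment has closed.

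No change is proposed for class A.

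The cost is one criterion and a wording change in an amendment, with no new tests. Some otherwise eligible subjects would be excluded; the documents do not allow their number to be estimated. A treated subject moved to 140 mg stays in the cohort's primary analysis population, as already happens when impairment develops on study.

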### 6.5.3 Criteria for Holding or Adjusting Dexamethasone

Up to three successive dose reductions of dexamethasone, from 40 mg to 20, 8, and 4 mg per week per investigator discretion, may be instituted for related toxicity which is unmanageable by supportive measures. Failure to tolerate 4 mg per week should lead to discontinuation of drug. Specific acute toxicities commonly noted with dexamethasone and other corticosteroids include upper gastrointestinal (dyspepsia, ulcer, gastritis), neurologic (confusion, mood alteration, insomnia), edema, hyperglycemia, and muscular weakness.

## 6.6 Criteria for Permanent Discontinuation of Study Drug

Investigators are encouraged to keep a subject who is experiencing clinical benefit (refer to [Section 4.1](#)) in the study unless significant toxicity puts the subject at risk or routine noncompliance puts the study outcomes at risk. If the subject meets any of the following criteria, then withdrawal from the study treatment is mandatory:

- Subject has confirmed PD.
- Subject has an intercurrent illness or AE that prevents further PCI-32765 capsule administration.
- Subject decides to withdraw from study or becomes pregnant.
- Subject is noncompliant with study procedures and/or scheduled evaluations.
- Subject requires a prohibited concomitant medication or bone marrow transplant.
- Investigator considers withdrawal to be in the best interest of the subject.
- Pharmacocyclics requires that the subject withdraw or Pharmacocyclics and/or regulatory authorities terminate the study.
- Subject completes the study.
- Subjects who withdraw for any reason after receiving the first dose of PCI-32765 will not be replaced. Subjects who withdraw prior to the first dose of PCI-32765 may be replaced.

### 6.6.1 Withdrawal of Consent

If a subject withdraws consent, it should be defined in the medical record if the subject withdraws consent to treatment and all further contact or if the subject withdraws partial consent,

ie, they no longer wish to receive treatment, but will participate in the Safety Follow Up Visit and/or Long term Follow up.

## **6.7 Concomitant Therapy**

### **6.7.1 Permitted Concomitant Therapy**

Antiemetics are permitted if clinically indicated. Standard supportive care medications are permitted. Use of hematopoietic growth factors is permitted in accordance with ASCO guidelines.

Short courses (<14 days) of corticosteroids (at dosages equivalent to prednisone  $\leq$ 20 mg per day) for treatment of non-cancer-related medical reasons are permitted.

### **6.7.2 Prohibited Concomitant Therapy**

Any chemotherapy, other myeloma-targeted therapy including “IMiDs” (eg, lenalidomide) and proteasome inhibitors (eg, bortezomib), anticancer immunotherapy, or corticosteroids are prohibited. Experimental therapy and radiotherapy to treat the underlying myeloma disease are prohibited.

Refer to [Section 6.8.1.1](#) for guidance on drugs that are CYP P450 inhibitors.

Refer to [Section 6.8.1.3](#) for guidance on use of anticoagulants.

### **6.7.3 Guidelines for PCI-32765 Management with Surgeries or Procedures**

PCI-32765 may increase risk of bleeding with invasive procedures or surgery. The following guidance should be applied during the perioperative period for subjects who require surgical intervention or an invasive procedure while receiving PCI-32765:

#### **6.7.3.1 Minor Surgical Procedures**

For minor procedures (such as a central line placement, needle biopsy, lumbar puncture [other than shunt reservoir access], thoracentesis, or paracentesis) PCI-32765 should be held for at least 3 days prior to the procedure and should not be restarted for at least 3 days after the procedure. For bone marrow biopsies that are performed while the subject is on PCI-32765, it is not necessary to hold CI-32765.

#### **6.7.3.2 Major Surgical Procedures**

For any surgery or invasive procedure requiring sutures or staples for closure, PCI-32765 should be held at least 7 days prior to the intervention and should be held at least 7 days after the procedure and restarted at the discretion of the investigator when the surgical site is reasonably healed without serosanguineous drainage or the need for drainage tubes.

### 6.7.3.3 Emergency Procedures

For emergency procedures, PCI-32765 should be held as soon as possible and until the surgical site is reasonably healed or for at least 7 days after the urgent surgical procedure, whichever is longer.

## 6.8 Precautions

For complete information on precautions refer to the IB.

### 6.8.1 Medications to be Used with Caution

#### 6.8.1.1 Concomitant Use of CYP Inhibiting/Inducing Drugs

Ibrutinib is metabolized primarily by CYP3A4. Avoid co-administration with strong CYP3A4 or moderate CYP3A inhibitors and consider alternative agents with less CYP3A inhibition.

- If a strong CYP3A inhibitor (eg, ketoconazole, indinavir, nelfinavir, ritonavir, saquinavir, clarithromycin, telithromycin, itraconazole, nefazadone, or cobicistat) must be used, reduce ibrutinib dose to 140 mg or withhold treatment for the duration of inhibitor use. Subjects should be monitored for signs of ibrutinib toxicity.
- If a moderate CYP3A inhibitor (eg, voriconazole, erythromycin, amprenavir, aprepitant, atazanavir, ciprofloxacin, crizotinib, darunavir/ritonavir, diltiazem, fluconazole, fosamprenavir, imatinib, verapamil, amiodarone, or dronedarone) must be used, reduce ibrutinib to 280 mg for those subjects receiving 840 mg and to 140 mg for those subjects receiving doses below 840 mg for the duration of the inhibitor use. For subjects who are already on moderate CYP3A inhibitor concomitantly with ibrutinib without significant toxicity the investigator may consider the overall risk-benefit to determine if a dose reduction of ibrutinib is appropriate. Avoid grapefruit and Seville oranges during ibrutinib treatment, as these contain moderate inhibitors of CYP3A (see [Section 6.3.1](#)).
- No dose adjustment is required in combination with mild inhibitors.

Avoid concomitant use of strong CYP3A inducers (eg, carbamazepine, rifampin, phenytoin, and St. John's Wort). Consider alternative agents with less CYP3A induction.

A list of common CYP3A inhibitors and inducers is provided in [Appendix 2](#).

For further information, please refer to the current version of the IB and examples of inhibitors, inducers, and substrates can be found at <http://medicine.iupui.edu/clinpharm/ddis/main-table/>. This website is continually revised and should be checked frequently for updates.

